18.0 Provisions to Monitor the Data to Ensure the Safety of Subjects*

Safety oversight for the study will be under the direction of the NCH IRB, as well as a Data Safety Monitoring Board (DSMB). The DSMB will consist of two faculty members from NCH. The first is a Professor of Pediatrics and Psychology at The Ohio State University and Director of the Biobehavioral Outcomes Core at NCH. She is a leading researcher in psychosocial outcomes among children and adolescents with significant health challenges, who has experience developing and executing intervention research with pediatric populations, as well as conducting multi-site studies involving complex multi-method longitudinal assessments. The second is an Associate Professor at The Ohio State University, an attending physician in Hematology/Oncology at NCH, director of the AYA Oncology Program, and a member of the Fertility and Reproductive Health team at NCH. He has been heavily involved in clinical research through the Children's Oncology Group, specifically in the enrollment and management of patients on clinical trials.

The DSMB will be responsible for safeguarding the interests of trial participants, assessing the safety and efficacy of the intervention(s) during the trial, and for monitoring the overall conduct of the clinical trial. The DSMB will periodically review study results, evaluate the study interventions and procedures for

adverse effects, and judge whether the overall integrity and conduct of the trial remain acceptable. Moreover, the DSMB may formulate and put forth recommendations to the study team, relating to the selection/recruitment/retention of participants and their management, and compliance to protocol specified regimens and the procedures for data management and quality control.

Summary reports regarding number of enrolled participants, and safety and risk (including any adverse events and unanticipated problems), will be generated at six-month intervals for the DSMB. Adverse events will be reported to the DSMB and IRB when they occur to determine if new procedures need to be implemented.

Safety information will be collected during routine interactions (phone calls, in-person visits, data collection timepoints) with participants.

Once the study begins, the study team will meet weekly to review the progress of the study (including information such as recruitment rate, reasons for declining participation, reasons for attrition), review data entry, assure data accuracy, detect potential errors at an early stage, and monitor staff compliance with training, regulatory, and confidentiality procedures.

The research will be suspended if the DSMB determines that is the best course of action, based on the data provided for review.

19.0 Adverse Events & Serious Adverse Events

Definitions: This protocol defines an adverse event (AE) as any negative physical or emotional condition that was not present at baseline. This protocol defines a serious adverse event (SAE) as any AE that results in hospitalization, permanent disability, or death.

Severity: All AEs and SAEs are assessed by the principal investigator, and if necessary, another professional with clinical experience in the study population to determine their severity.

For AEs and SAEs, the following guidelines are used to describe severity:

- Mild: Events require minimal or no treatment and do not interfere with the participant's daily activities.
- Moderate: Events result in a low level of inconvenience or concern with the therapeutic measures. Moderate events may cause some interference with functioning.
- Severe: Events interrupt a participant's usual daily activity and may require systemic drug therapy or other treatment. Severe events are life-threatening or incapacitating.

Relationship to the Intervention: All AEs and SAEs are assessed by the principal investigator, and if necessary, another professional with clinical experience in the study population to determine their relationship to study intervention. The evaluation of relatedness considers etiologies such as natural history of the underlying disease, concurrent illness, concomitant therapy, study-related procedures, accidents, and other external factors.

The degree of certainty about causality is graded using the following categories:

• Related: The event is known to occur with the study procedures, there is a reasonable possibility that the study procedures caused the event, or there is a temporal relationship between the study procedures and the event. Reasonable possibility means that there is evidence to suggest a causal relationship between the study procedures and the event.

• Not Related: There is not a reasonable possibility that the study procedures caused the event, there is no temporal relationship between the study procedures and event onset, or an alternate etiology has been established.

Expectedness: All AEs and SAEs are assessed by the principal investigator, and if necessary, another professional with clinical experience in the study population to determine their expectedness. Expectedness is assessed based on the awareness of AEs and/or SAEs previously observed, not on the basis of what might be anticipated from the properties of the study intervention.

Expectedness of the event is assessed using the categories below:

- Expected: An event is considered expected if the nature, severity, or frequency of the event is consistent with the risk information previously described for the study procedures.
- Unexpected: An event is considered unexpected if the nature, severity, or frequency of the event is not consistent with the risk information previously described for the study procedures.

Time Period and Frequency for Event Follow-up: Research staff record events with occurring after informed consent is given up until the end of the intervention. The occurrence of AEs and/or SAEs may come to the attention of study personnel during study visits, interviews, and questionnaires; or when a study participant presents for medical care.

AEs and SAEs are captured on the appropriate case report form (CRF). Information collected includes event description; time of onset; clinician assessment of severity, relationship to study procedures (assessed only by those with the training and authority to make a diagnosis), expectedness; and time of resolution/stabilization of the event. All AEs and SAEs occurring during the above-mentioned timeframe are documented appropriately regardless of relationship to the intervention. Events are followed for outcome information until resolution or stabilization.

Reporting: AEs are reported to the NCH IRB at least annually. AEs are reported to the DSMB at each meeting. AEs are reported to NCI according to their recommended timelines. Per NCH HRP-103 (updated 12/10/18), SAEs determined to be related to the intervention and unexpected are reported to the NCH IRB within 5 business days of discovery; other SAEs are reported to the NCH IRB annually. SAEs are reported to the DSMB and to NCI according to their recommended timelines.

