14.0 Withdrawal of Subjects*

Participants may be withdrawn if the intervention causes distress and it is determined by the interventionist and/or medical team that is not in the participant's best interest to continue. If the participant withdrawals from the intervention, study staff will encourage completion of study data collection, per intent-to-treat methodology.

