15.0 Risks to Subjects*

It is expected that completing study questionnaires and interviews will introduce minimal risk to participants, yet the study team acknowledges that the new cancer diagnosis will be a stressor for AYAs and parents. Participants may experience some discomfort and/or embarrassment when completing survey items or interviews about FP. Given the study design, all patients and caregivers will have already received information about FP during the clinical fertility consult, per standard of care. Parents or AYAs may experience distress when asked about parent-child communication, although we do not expect this to have severe or long-lasting effects on the respondent. In preliminary work, parents and AYA have completed measures, similar to those in this study, within 10 minutes and provided positive feedback about the experience, emphasizing their perceived importance of addressing this topic. Loss of confidentiality is also a potential risk, although no more so than in any other research study. The study team will take every precaution to prevent this.

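### Read literally, the adverse-event definition in Section 19.0 leaves out worsening of a condition that already existed, so worsened distress may go unrecorded or be recorded inconsistently

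*Combined protocol and SAP*

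**What the plan says.** Section 19.0 defines an AE as "any negative physical or emotional condition that was not present at baseline". It defines an SAE as "any AE that results in hospitalization, permanent disability, or death". Events that qualify are then graded for severity, relationship to the study procedures and expectedness, entered on a case report form, and reported to the IRB, the DSMB and the funder.

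Section 15.0 describes the expected state of participants: "the study team acknowledges that the new cancer diagnosis will be a stressor for AYAs and parents". It then lists risks from the study itself. On the questionnaires and interviews it says: "Participants may experience some discomfort and/or embarrassment when completing survey items or interviews about FP". On communication it says: "Parents or AYAs may experience distress when asked about parent-child communication", and adds "although we do not expect this to have severe or long-lasting effects on the respondent". It also names loss of confidentiality.

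Section 14.0 opens: "Participants may be withdrawn if the intervention causes distress", subject to a judgement by the interventionist or the medical team about the participant's interest.

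In the severity scale of Section 19.0, the top grade includes this sentence: "Severe events are life-threatening or incapacitating".

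**The concern.** The usual purpose of an AE definition is to catch any unfavourable change after entry. This one tests only whether the condition was absent before. A change in degree does not count.

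That would matter little in a healthy sample. Here, families are approached straight after the fertility consult and before cancer treatment (Section 13.0), when some distress is to be expected in both patients and caregivers. A conversation that made existing distress worse is a harm that the protocol takes seriously enough to allow withdrawal, yet its own definition may keep that harm off the AE form. The DSMB's six-monthly summaries and the annual IRB report would then be incomplete on this kind of event. A statement that no related AEs occurred would not show that distress had not worsened.

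**Working it through.** No arithmetic applies. The check is to apply the definition to plain cases and then look for any text that widens it.

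**Step 1: apply the definition.**

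| State at baseline | After study procedures | AE as written? | SAE if hospitalized? |
|---|---|---|---|
| Not distressed | Distressed | Yes | Yes |
| Distressed | More distressed | No, on the literal reading | No, because an SAE must first be an AE |
| Distressed about the diagnosis | Also distressed about the study topics | Depends on whether the assessor calls it a separate condition | Same |

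The second row is the gap. The third is where two assessors could differ.

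**Step 2: look for a widening clause.** Sections 14.0, 15.0 and 18.0 to 20.0 contain no reference to worsening, exacerbation or increased severity of an existing condition. The grading scales in Section 19.0 apply to events that already qualify as AEs, so they do not widen the definition. The rule in the same section that events are documented whatever their relationship to the intervention also presupposes an AE.

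**Step 3: can baseline status be established?** Section 6.0 lists consent, demographics (with four communication questions for the patients) and randomization at Visit 1. No measure of distress is described. Whether a condition was absent at baseline is therefore a matter of judgement, and the protocol does not say whose or on what evidence.

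**Step 4: do other routes capture the event?**

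- Unanticipated problems (Section 20.0) cover psychological harm, but an event must be unexpected, at least possibly related, and suggestive of more risk than was known. Distress of the kind foreseen in Section 15.0 would normally fail the first and third tests.
- Referral to the psychosocial provider (Section 6.0, Risk Minimization) is support and creates no AE record.
- Reasons for attrition are reviewed weekly (Section 18.0), but by the study team.
- The DSMB's six-monthly reports cover safety and risk, with AEs and unanticipated problems among their contents (Section 18.0). Nothing there requires worsened distress to be listed.

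**Step 5: the severity scale and the SAE definition.** The top severity grade names life-threatening events. The three SAE outcomes are hospitalization, permanent disability and death. A life-threatening event with none of these outcomes would be graded severe but would not be an SAE.

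**The case against.** The best defence is that distress caused by the session is, by its nature, new. Visit 1 data are collected before the intervention begins (Section 6.0, Data Collection Procedures). Section 15.0 also separates the stress of the diagnosis from discomfort with fertility questions or distress about family communication. On that reading a withdrawal under Section 14.0 would usually have an AE behind it. This is a fair reading, and it defeats the inference that a participant withdrawn for distress necessarily has no AE to record. It does not close the gap, because the text does not adopt it and a more literal assessor could decide otherwise.

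Oversight is also wider than AE counts. The DSMB is asked to look for adverse effects generally, safety information comes from all routine contacts, acceptability has its own survey, and the interviews ask about the effect of taking part. A reader might infer that the trial could declare the intervention safe and acceptable on AE counts alone. The documents do not support that.

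Two further inferences go too far. One is that distress is the main, or only, foreseeable harm: Section 15.0 does not rank its risks, names others, and expects the distress to be neither severe nor lasting. The other is that a stated share of all participants could not register harm: the documents give no rate of distress at baseline, and only the intervention arm has a session.

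Finally, Section 19.0 records events only up to the end of the intervention, a session designed to last under 20 minutes (Section 5.0). If that window is literal, later worsening stays outside AE recording whatever the definition says. That is a separate question, but it limits what this fix achieves alone.

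**Conclusion.** The point holds as a gap in the stated rule. On its literal terms Section 19.0 excludes worsening of an existing physical or emotional condition from AEs, and therefore from SAEs, and no other section restores it. In families whom the protocol expects to be under stress already, worsened distress could be missed or recorded inconsistently. The conclusion rests on the wording alone and on no assumed rate. Its size cannot be given as a number, and the other safety routes soften the consequence. It should be corrected because the remedy is simple and improves safety recording.

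A secondary point stands apart from this. The SAE definition omits life-threatening events, which the severity scale names. A reader might infer that the two must match. They need not, since severity and seriousness are different classifications. But the omission is not explained, and the two texts should be reconciled.

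**What to change.** In Section 19.0, define an AE as any negative physical or emotional condition that is new, or that worsens in severity or frequency from baseline. State that baseline means the participant's condition before the intervention (for controls, the corresponding point of Visit 1), as judged by the assessor or reported by the participant. This avoids adding a questionnaire at a difficult time. In Section 14.0 or 19.0, state that any withdrawal for distress caused by the intervention is recorded as an AE.

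Separately, the sponsor should reconcile the SAE definition with the severity scale on life-threatening events.

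The cost is a few sentences in the protocol, a matching change to the AE form, and a somewhat higher AE count in both arms. How much higher depends on how the recording window is read: under a wide reading, worsening physical conditions in patients starting cancer treatment would also be entered, whatever their cause. The sponsor should therefore confirm the window when making the change.

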This study seeks to improve FP in AYA males newly diagnosed with cancer by designing and evaluating the feasibility, acceptability, and preliminary efficacy of a family-centered psychoeducational intervention to optimize FP uptake and decision quality. To this effect, we will employ a blinded design. Both control and experimental groups will be pulled from one population (males with new cancer diagnoses) to control for biases and individual differences. Participants will be randomized and staff who consent families and conduct data collection activities will be blind to treatment group. The CBH Behavioral Trials Office (BTO) will maintain the randomization sequence and randomization to study group will be implemented through the data management software REDCap, which allows the randomization sequence generated by the statistician to be allocated via REDCap Randomization Module. In this module, the randomization sequence and group assignments are protected from the view of selected staff who use the REDCap program. Only BTO staff will have REDCap permissions to see the randomization sequence. Only the interventionist will have REDCap permissions to randomize and see the allocated group assignment when they log-on to REDCap. Outcome assessors (RAs) and investigators will be blinded to the intervention and will not have access to treatment allocation information in REDCap.

Baseline (Visit 1): At baseline (Visit 1), research staff will approach families in-person (at inpatient or outpatient clinic) or via phone, Webex, or email. Families (AYAs and parents) will receive a short briefing on the purpose of the study, provide informed consent, and staff will administer baseline measures after the family has consented to participate in the study. All measures will be completed by the child and both caregivers (when available). In the event that one family member is unable to participate or declines participation, the other family member(s) will be allowed to enroll separately. If a caregiver is only available remotely, a REDCap link to the survey will be provided electronically, and the caregiver will be included in the intervention remotely (e.g. via phone). If the entire family is only available remotely, participants will be contacted via phone and will be emailed a Webex link and REDCap links to participate in the study. The activities completed at Visit 1 are:

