13.0 Recruitment Methods

At Nationwide Children's Hospital (NCH), every patient with a new cancer diagnosis has an automatic referral placed to the multidisciplinary Fertility and Reproductive Health Team. The oncofertility navigator meets with the patient and family to assess pubertal status and achievement of sexual milestones (masturbation), review infertility risk, present FP options, and discuss logistics (including cost). After the oncofertility navigator completes the consult and introduces the study to the family, the study team will approach those who are eligible and invite their participation. Study staff will primarily recruit in person, in clinic. As the first assessment will occur immediately after the fertility consult (before cancer treatment), most AYA have two parents present. If participants are unavailable at times of appointments or admissions, study staff may contact families via telephone or email.

If a participant is not present during the time of in person recruitment, but is available remotely, study staff will obtain contact information from the present participants and will initiate a phone call. The study staff will then go through recruitment with the participant over the phone or via Webex.

- *Incentives:* Families will receive the following incentives for their participation (participants approached in person will receive their incentive at the conclusion of a visit. Participants approached remotely will receive incentives via mail):
 - Baseline: \$10 ClinCard for each participant
 - 1-month follow-up: \$20 ClinCard for each participant
 - 1-year follow-up: \$30 ClinCard for each participant

Retention: Based on our previous work, engagement at 1-month post intervention is 100% due to patients actively being on treatment for their cancer diagnosis, routine clinical follow-up appointments, and other treatment-related in and outpatient encounters taking place at Nationwide Children's Hospital. Therefore, we anticipate similarly high retention in this study. However, additional strategies will be used to keep families engaged throughout the study, including the 1-year post-intervention follow up. These include:

- Coordinating follow-up appointments with already scheduled clinic visits
- Routine correspondence with their medical team, and checks of the NCH electronic medical record for updated contact information or upcoming appointments within the hospital
- Check-in phone calls, emails, and/or text messages

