20.0 Unanticipated Problems

Definition: This protocol uses the definition of Unanticipated Problems as defined by the Office for Human Research Protections (OHRP). OHRP considers unanticipated problems involving risks to participants or others to include, in general, any incident, experience, or outcome that meets all the following criteria:

- Unexpected in terms of nature, severity, or frequency given (a) the research procedures that are described in the protocol-related documents, such as the Institutional Review Board (IRB)-approved research protocol and informed consent document; and (b) the characteristics of the participant population being studied;
- Related or possibly related to participation in the research ("possibly related" means there is a reasonable possibility that the incident, experience, or outcome may have been caused by the procedures involved in the research); and
- Suggests that the research places participants or others at a greater risk of harm (including physical, psychological, economic, or social harm) than was previously known or recognized.

Reporting: Unanticipated problems (UPs) are reported by the PI to the Institutional Review Board (IRB) and the DSMB within 5 business days of discovery. SAEs are initially reported to NCI within five calendar days, with a full report filed within 10 calendar days.

21.0 **Provisions to Protect the Privacy Interests of Subjects**

Plan to Protect Participant Privacy: Participant confidentiality and privacy is strictly held in trust by the participating investigators, their staff, the safety and oversight monitor(s), and the funding agency. This confidentiality is extended to the data being collected as part of this study. Data that could be used to identify a specific study participant will be held in strict confidence within the research team. No personally-identifiable information from the study will be released to any unauthorized third party without prior written approval of the funding agency.

All research activities will be conducted in as private a setting, as much as possible.

Authorized representatives of the sponsor, study monitors, representatives of the Institutional Review Board (IRB), or regulatory agencies may inspect all documents and records required to be maintained by the investigator. The clinical study site will permit access to such records.

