26.0 Setting

Research will be conducted at a single-site, Nationwide Children's Hospital (Columbus, OH). After an initial and new cancer diagnosis, an automatic referral is placed for a fertility consult and [name] is immediately notified of the age and sex of the patient. The patient and family then consult with a fertility navigator to discuss fertility options, per standard of care. During the fertility consult the fertility navigator will assess pubertal status/eligibility for sperm banking, provide verbal and written information about infertility risk and FP options (masturbation/sperm extraction), and then introduce the study. The

patient's eligibility is communicated to study staff who then approach the family for recruitment purposes.

All study procedures except interviews will take place in the patient's hospital room (or clinic room), or other private location at Nationwide Children's Hospital. Interviews will be carried in private consultation rooms on the treatment floors, or other private location at Nationwide Children's Hospital. In the event that a parent (or the entire family) is not present, surveys or interviews may be administered over the phone or via Webex.

27.0 **Resources Available**

Feasibility: There are approximately 30 males newly diagnosed with cancer in our target age range each year. Taking into account our inclusion/exclusion criteria, infrastructure of the fertility consult service, and recruitment rates in our pilot (>90%), we anticipate completing our recruitment goals within the allocated timeframe.

Time Devoted to the Research: [name] assembled a multidisciplinary team with expertise in mixed methods research; family systems and communication; and the design, implementation, and analysis of clinical trials to support and carry out this project.

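### The SAE definition omits life-threatening events and prolonged admission, so a survivable life-threatening event in an already admitted AYA need not be an SAE

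*Combined protocol and SAP*

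**What the plan says.** Section 19.0 (Definitions) treats as an AE "any negative physical or emotional condition that was not present at baseline". It then "defines a serious adverse event (SAE) as any AE that results in hospitalization, permanent disability, or death". That list is complete: no other section adds a criterion.

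The severity scale in section 19.0 has three grades. Of the top one it says: "Severe events are life-threatening or incapacitating". The grade is not linked to SAE status.

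On setting, section 6.0 (Baseline, Visit 1) says "research staff will approach families in-person (at inpatient or outpatient clinic) or via phone, Webex, or email". Section 26.0 places study procedures in the hospital or clinic room. Section 13.0 adds: "Study staff will primarily recruit in person, in clinic". No section gives the proportion enrolled as inpatients.

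Several reporting rules turn on the SAE label:
- **NCI:** section 20.0 states that "SAEs are initially reported to NCI within five calendar days, with a full report filed within 10 calendar days".
- **IRB:** under section 19.0, SAEs that are both related and unexpected go to the IRB within 5 business days; other SAEs go annually.
- **Other AEs:** section 19.0 sends these to the IRB at least once a year, and to NCI on NCI's own timelines with no number of days stated. Section 18.0 instead has AEs reported to the DSMB and IRB at the time they happen.

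**The concern.** Apart from death and permanent disability, the only way an event becomes serious is by causing an admission. That criterion cannot operate for a patient who is already admitted, and this population is newly diagnosed with cancer and may be in hospital when approached. Neither of the two criteria that would take its place for an inpatient, a threat to life or a lengthened stay, is in the definition.

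The AE definition also covers emotional events, and section 14.0 allows for withdrawal when the intervention causes distress. An acute psychological crisis with a threat to life in an inpatient would fall into the same gap.

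At stake is whether such an event appears in the SAE count and reaches NCI and the IRB on the SAE timetable.

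**Working it through.** The plan states no figure on this point and no arithmetic applies. The check applies the definition to one event in two settings: a new life-threatening event, within the recording window, survived without permanent disability.

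| Rule | Outpatient at consent, then admitted because of the event | Inpatient at consent |
|---|---|---|
| Severity grade (19.0) | Severe | Severe |
| Results in hospitalization? | Yes | No, already admitted |
| Permanent disability? | No | No |
| Death? | No | No |
| SAE under 19.0? | **Yes** | **No, even if the stay is lengthened** |
| NCI | Initial report in 5 calendar days, full report in 10 (20.0) | AE timelines recommended by NCI, no days stated (19.0) |
| IRB, if related and unexpected | 5 business days as an SAE (19.0) | No SAE route; see below |

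The event is the same; the classification differs only because of where the patient was at consent.

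Three other routes could carry the inpatient event:

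1. **Unanticipated problem (20.0).** This reaches the IRB and DSMB within 5 business days. The event must be unexpected, at least possibly caused by the research, and suggestive of greater risk than was known. Section 19.0 accepts a temporal relationship alone as related, whereas section 20.0 asks for a reasonable possibility of causation. An unexpected event related only by timing would therefore get the 5-business-day report as an SAE, yet need not qualify here. The NCI deadlines in section 20.0 are written for SAEs.
2. **AEs reported as they occur (18.0).** Read alone, this brings the event to the DSMB and IRB promptly. It disagrees with the at-least-annual rule in section 19.0, so it is uncertain which governs. It does not mention NCI.
3. **Immediate contact with the PI (6.0, Risk Minimization, and 27.0).** Staff alert the PI to any adverse event, with IRB notification if necessary. This secures attention but not classification or a deadline.

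How often the gap would matter depends on the recording window. Section 19.0 records events from consent to the end of the intervention. Baseline measures and randomization come first; the intervention follows at once (6.0) and is meant to take under 20 minutes (5.0). The risks listed in section 15.0 are discomfort, embarrassment, distress and loss of confidentiality. Events starting in that window are then followed to resolution or stabilization, so a lengthened stay would be seen but would not change the classification.

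**The case against.** The strongest reply is that little is lost in practice. SAE status speeds IRB reporting only for events that are related and unexpected. A related, unexpected, life-threatening event in a minimal-risk behavioural study would very probably also be an unanticipated problem, with the same 5-business-day deadline. For all other events the SAE label gives the IRB nothing faster than the AE rule does. This largely stands for the IRB. It does not restore the SAE count or the NCI deadlines, and it leaves the case related only by timing.

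A second reply is that severity and seriousness are different concepts. That is correct. A reader might infer that the severity scale contradicts the SAE definition; it does not. The scale shows only that the protocol foresees life-threatening events without giving them an SAE route.

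Two other stronger readings are not supported:

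- **That many families are enrolled as inpatients.** The documents establish only that they may be, and section 13.0 points to clinic as the main setting. Assuming a 25% to 75% inpatient share gives 0.25 × 40 = 10 to 0.75 × 40 = 30 AYAs. Those shares are assumptions, and the result counts admitted patients, not misclassified events.
- **That such an event would reach the IRB only once a year.** Section 18.0, the duty to contact the PI and the unanticipated-problem route all point to earlier notice.

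Finally, if the recording window were read broadly, because section 18.0 gathers safety information at all data collection timepoints, prolonged stays in this population could add SAE reports. That is a fair caution about cost. New admissions already count as SAEs whatever their cause, so the addition is of the same kind as what the protocol already collects.

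**Conclusion.** The gap is real but narrow. As written, a new life-threatening event in an already admitted AYA who survives without permanent disability need not be an SAE. It would then miss the SAE count, the 5- and 10-calendar-day NCI reports and, if related and unexpected, the SAE route to the IRB. The existing safeguards cover part of this, mainly on the IRB and DSMB side, and one of them is weakened by the disagreement between sections 18.0 and 19.0.

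The number of affected events cannot be calculated from the documents. It is expected to be very small, on the assumptions that the recording window is applied as section 19.0 states and that the risks are those in section 15.0. The conclusion needs only that inpatient enrolment is permitted. This is a cheap improvement to safety classification, not a flaw that threatens the trial's results.

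**What to change.** - In section 19.0 (Definitions), and on the AE form, extend the SAE definition to AEs that are life-threatening or that prolong an existing hospitalization.
- Reconcile sections 18.0 and 19.0 on when AEs are reported to the IRB, so that one rule applies.

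The cost is one line in the protocol, a matching change to the form, and possibly a few additional SAE reports. No visit, measure or analysis changes.
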